#### 5. INVESTIGATIONAL PLAN

##### a. Study Design

The study will use a single-arm, post-test-only trial design to examine the feasibility and acceptability of the intervention and estimate of patient and caregiver outcomes in 7 and 30 days after SNF discharge.

Study phases: The study team will use a limited waiver of HIPAA authorization to pre-screening for patient and caregiver eligibility during the SNF admission. The study team will recruit SNF patients and their caregivers in-

person (or, when risk mitigation related to COVID-19 prevents in-person contact, we will recruit virtually, using an iPad and connection via ZOOM) within 10 days of their admission and will review the patient's medical record to confirm eligibility. The study team will obtain written consent (or, when risk mitigation related to COVID-19 prevents in-person contact, they will obtain verbal consent) of SNF patients and their caregivers. The study team will collect baseline data during the SNF admission. SNF patients and caregivers will receive the Connect-Home Plus intervention in the SNF admission and the SNF caregivers will receive the intervention by telephone in 30 days after SNF discharge. The study team will collect outcome data from the patient and caregiver (or from the caregiver only if the patient is not able to participate in data collection) in 7, 21, and 30 days after SNF discharge. The chart review of medical records will occur in 30 days after SNF discharge.

**b. Study Duration**

Participants will be recruited during the SNF stay, when baseline data will be collected, and they will participate in the study for up to 60 days post-discharge. The entire study is expected to last 12 months.

**c. Enrollment and Number of Subjects**

20 persons with ADRD and their 20 caregivers in 2 SNFs

**d. Study Population**

Patient Inclusion Criteria:

- be able to speak English
- have a goal of discharge to home
- have a diagnosis of ADRD, or a Brief Inventory of Mental Status (BIMS) score <13, or (for persons unable to complete the BIMS assessment), have a Cognitive performance score of  $\geq 3$  (calculated using data in the Minimum Data Set 3.0 and an algorithm for estimating cognitive impairment using Minimum Data Set 3.0 data other than BIMS).(25)
- have a caregiver willing to participate.
- for patients with documentation in the medical record of a caregiver who is the patient's legally authorized representative, consent of the caregiver to participate in the study as the patient's representative.

Patient Exclusion Criteria:

- be unable to speak English

Caregiver Inclusion Criteria:

- self-report assisting the patient at home
- be able to speak English.

Caregiver Exclusion Criteria:

- be unable to speak English

**6. STUDY PROCEDURES**

The study team will use a limited waiver of HIPAA authorization to pre-screening for patient and caregiver eligibility during the SNF admission. The study team will recruit SNF patients and their caregivers in-person (or, when risk mitigation related to COVID-19 prevents in-person contact, we will recruit virtually, using an iPad and connection via ZOOM) within 10 days of their admission and will review the patient's medical record to confirm eligibility. The study team will obtain written consent (or, when risk mitigation related to COVID-19 prevents in-person contact, they will obtain verbal consent) of SNF patients and their caregivers. The study team will collect baseline data during the SNF admission. SNF patients and caregivers will receive the Connect-Home Plus intervention in the SNF and the SNF caregivers will receive the intervention after the SNF discharge in a home visit

with the home care nurse and in telephone calls with the dementia caregiving specialist in 30 days after SNF discharge. The study team will collect outcome data from the patient and caregiver (or from the caregiver only if the patient is not able to participate in data collection) in 7, 21, and 30 days after SNF discharge. The chart review of medical records will occur in 30 days after SNF discharge.

a. Screening/Baseline Visit procedures

For persons with ADRD, inclusion criteria are: (1) be able to speak English; (2) have a goal of discharge to home; (3) have a diagnosis of ADRD, or a BIMS score <13, or (for persons unable to complete the BIMS assessment) a CPS of  $\geq 3$  (calculated using data in the Minimum Data Set 3.0 and an algorithm for estimating cognitive impairment using Minimum Data Set MDS data other than BIMS (26, 27)); and (4) have a caregiver willing to participate. We will recruit a representative for persons with ADRD who have a legally authorized representative (LAR); in addition, we will recruit a family caregiver to represent persons admitted to the SNF who are not able to complete the BIMS or who have a BIMS score  $\leq 7$ . Exclusion criterion for patients: planned hospital readmission for procedures/treatments in next 30 days (thus distorting assessment of patient and caregiver outcomes). Inclusion criteria for caregivers: 1) self-reports assisting the patient at home; and 2) the ability to speak English. We will identify caregivers using documentation in the medical record that the caregiver provides care at home and/or is legally authorized representative of the person with ADRD. We will use procedures from the Connect-Home parent study to recruit staff, persons with ADRD, and caregivers. To recruit persons with ADRD and caregivers, a Research Coordinator (RC) will use a HIPAA waiver allowing prescreening for eligibility and will: 1) consult the nursing director in each SNF to identify persons admitted to the SNF; and 2) screen the medical record of persons with ADRD who are expected to be discharged home. Using IRB approved forms and consent procedures, the RC will recruit persons with ADRD and caregivers in-person or by phone during the SNF stay until the recruitment goal is reached. The RC will recruit staff using procedures from the parent study. All participants will give written informed consent for study participation.

The RC will administer baseline enrollment surveys to collect measures of co-variates while the person with ADRD is in the SNF, or from the caregiver or legally authorized representative of the person.

b. Intervention/Treatment procedures (by visits)

Connect-Home Plus is a two-step transitional care intervention: 1) SNF staff create an individualized Transition Plan or Care and prepare the patient with ADRD and caregiver to manage the patient's illness at home; and 2) within 3 days of discharge a home care nurse visits the patient and caregiver at home and within 30 days of SNF discharge, a dementia caregiving specialist calls the caregiver three times at home and helps them implement the written Transition Plan of Care. Both intervention steps focus on 6 key care needs to optimize patient and caregiver outcomes: 1) home safety and level of assistance; 2) advance care planning; 3) symptom management; 4) medication reconciliation; 5) function. See **Section 5** for additional detail.

c. Follow- up procedures (by visits)

Schedule of Activities for Patients:

See next page

Assessments and Procedures	Screen	Pre Discharge	Discharge	1-3 days post discharge	7 Days Post-Discharge (+ 10/- 3 days)	21 Days Post-Discharge (+/- 7 days)	30 Days Post-Discharge (+/- 7 days)
Informed Consent	X						
Confirm Eligibility	X						
Baseline interview		X					
Chart Abstraction					X		
Connect-Home in SNF		X					
Home Care Nurse visits				X			
CTM-15					X		
Satisfaction interview						X	
DEMQoL							X
Life Space Assessment							X
Chart Abstraction							X
Hospital and ED use assessment							X

Schedule of Activities for Caregivers:

Assessments and Procedures	Screen	Pre Discharge	Discharge	1-3 days post discharge	7 Days Post-Discharge (+ 10/- 3 days)	21 Days Post-Discharge (+/- 7 days)	30 Days Post-Discharge (+/- 7 days)
Informed Consent	X						
Confirm Eligibility	X						
Baseline interview		X					
Connect-Home in SNF		X					
Home Care Nurse visits				X			
Readiness for Caregiving assessment					X		
Dementia Caregiving Specialist calls				X	X	X	
Satisfaction interview						X	
DEMQoL-proxy assessment							X
Caregiver burden and distress assessment							X

d. Subject Completion/ Withdrawal procedures

All identifying information will be destroyed at the earliest possible time following completion of the study. In addition, data will be reported in aggregate form, without identifying information by site or individual. Publications arising from the study will not contain personal information.

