### 7. STUDY EVALUATIONS AND MEASUREMENTS

#### Data Collection Procedures

The research coordinator (RC) will administer baseline enrollment surveys to collect measures of co-variates while the person with ADRD is in the SNF, or from the caregiver or legally authorized representative of the person. Second, the RC will collect outcome data by phone from persons with ADRD and caregivers in 7, 21, and 30 days after SNF discharge. Finally, also using procedures from the parent study, after a patient's discharge from the SNF, the RC will use a standardized tool to abstract data from the medical record in the SNF and the RC will audit the log maintained by the dementia caregiving specialist (study staff) who will make the caregivers calls after the patient discharges from the SNF.

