#### Variables that will be abstracted from the intervention log maintained by the dementia caregiving specialist (study staff)

As part of Connect-Home Plus, a dementia caregiver specialist will maintain a written log of details from supportive calls with the caregiver after the patient transfer from SNF to home, including one post-discharge support call within 72 hours after discharge and two additional calls within one month of discharge. Data collected from the Call-back log will include: number of days after discharge on which the call occurred, duration of the call, transition challenges identified on the call, caregiver education provided on the call, and follow-up actions and next steps identified on the call.

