  - Important medical event based upon appropriate medical judgment

Potential sources of information for identification of AEs include (but may not be limited to) nursing home staff reports of events while the patient is in the nursing home, and patient or caregiver reports of events while the patient is in the nursing home or at home. For example, the proposed study team will be in contact with the patient and caregiver over 30 days after the patient discharges from the nursing home to home. We will be calling the patient and caregiver at 7, 21 and 30 days. Any event that is discovered will be immediately relayed to the PI, or if he is away, another member of the research team so that we can execute safety plans and reporting plans described here.

AEs will be labeled according to severity, which is based on their impact on the patient. An AE will be termed 'mild' if it does not have an impact on the patient, 'moderate' if it causes the patient some minor inconvenience

and ‘severe’ if it causes a substantial disruption to the patient’s well-being. AEs will be categorized according to the likelihood that they are related to the study intervention. Specifically, they will be labeled either definitely, probably, possibly or unrelated to the study intervention. If any IRB actions occur, the PI will email a report within 24 hours for the Independent Monitor, the second Independent monitor, and the Program Officer in the NINR in accordance with requirements.

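### The follow-up windows overlap, and the 30-day call may be made from day 23, so up to 7 of the 30 days of acute-care use and events can go unobserved

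*Combined protocol and SAP*

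**What the plan says.** The patient and caregiver schedules in Section 6c carry the same three follow-up headings: "7 Days Post-Discharge (+ 10/- 3 days", "21 Days Post-Discharge (+/- 7 days" and "30 Days Post-Discharge (+/- 7 days".

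Each contact has its own instruments:
- **7-day:** CTM-15 for the patient and the preparedness (readiness) assessment for the caregiver.
- **21-day:** the satisfaction interviews.
- **30-day:** quality of life, Life Space Assessment, caregiver burden and distress, and hospital and emergency department use.

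Section 7 (Data Collection Procedures) says that "the RC will collect outcome data by phone from persons with ADRD and caregivers in 7, 21, and 30 days" after discharge. Section 7 (Outcome Measures) defines the acute-care outcome as self-reported days in the emergency department or hospital in the 30 days after SNF discharge.

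The safety text in Section 7a gives these calls as its example of how the team stays in contact over 30 days: "We will be calling the patient and caregiver at 7, 21 and 30 days". It adds that "Any event that is discovered will be immediately relayed to the PI", and it lists "patient or caregiver reports of events while the patient is in the nursing home or at home" among its sources of adverse-event information. The same section counts inpatient hospitalization as a serious adverse event.

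No section requires the calls to occur in order, sets a minimum interval, or assigns a call that falls in two windows.

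**The concern.** A tolerance around a target day is normal. It becomes a problem when it lets the assessment happen before the period it is meant to cover has ended. The acute-care outcome is a count over a fixed 30 days, collected once, by recall, at the 30-day contact. If that contact is on day 23, the participant cannot report days 24 to 30, and the summary combines counts over different lengths of follow-up under one 30-day label. The error runs one way: unobserved days can only lower the count.

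The same applies to adverse events. The safety text relies on contact over 30 days, and the last scheduled call in that series can come a week short. A hospital admission on day 26 could be missing from both the outcome and the serious adverse event listing.

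The overlap itself is a smaller matter of bookkeeping: a call on day 15 or day 25 belongs to two windows. The wide first window also means that preparedness described as a 7-day result may have been measured on any of 14 different days.

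**Working it through.** The plan states no derived figure to reproduce, and no power or alpha calculation applies, because the study is descriptive.

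**Windows** (targets and tolerances from Section 6c, identical in both schedules)
- 7-day: 7 - 3 = 4 to 7 + 10 = 17, so days 4-17 (14 days)
- 21-day: 21 - 7 = 14 to 21 + 7 = 28, so days 14-28 (15 days)
- 30-day: 30 - 7 = 23 to 30 + 7 = 37, so days 23-37 (15 days)

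**Overlaps**
- First and second: days 14-17 (4 days)
- Second and third: days 23-28 (6 days)
- First and third: none, since 17 < 23

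Neighbouring calls can therefore share a day or reverse order. For example, the 21-day call can be on day 14 and the 7-day call on day 17, or the 30-day call on day 23 and the 21-day call on day 28. Of the 14 x 15 x 15 = 3,150 whole-day combinations, 90 put the 7-day call after the 21-day call and 210 put the 21-day call after the 30-day call. These counts show what is allowed. They are not probabilities.

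**Days missed by an early 30-day call**
- Missed days = 30 - call day, for calls before day 30
- Day 23: 30 - 23 = 7, or 7/30 = 0.23 of the outcome period
- Day 29: 30 - 29 = 1
- Calls on days 23-29 fall short, which is 7 of the 15 permitted days

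**Illustration of size.** The Relevant Literature section cites 23% rehospitalization within 30 days of returning home among persons with ADRD. Assume that this rate applies to the 20 patients and that admissions are spread evenly over the 30 days. The documents support neither assumption directly.
- Expected patients readmitted: 0.23 x 20 = 4.6
- All calls on day 23: 4.6 x 7/30 = 1.1 patients with the admission unobserved
- All calls on day 26: 4.6 x 4/30 = 0.6
- All calls on day 29: 4.6 x 1/30 = 0.2
- All calls on day 30 or later: 0

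The range is 0 to about 1 patient in 20. It would be lower if admissions cluster soon after discharge. It leaves out patients already in hospital at the call, whose later hospital days would also be uncounted.

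**Timing of the preparedness scales.** The latest in-window assessment is day 17, which is 17 - 7 = 10 days after the nominal day.

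**The case against.** The strongest reply is that these are permitted extremes in a small descriptive pilot, and that much of what one might infer from the overlap does not follow. Most of that reply stands.

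- **Order changes no estimate.** No instrument is repeated across the three calls, and no change score or time trend is planned. Reversed order alone biases nothing.
- **Day 17 is not the latest first contact.** A reader might infer that participants could go unobserved until day 17. The documents do not support that. A home nurse visits within 24 hours or 3 days, depending on the section, and the specialist, who is study staff, makes "one post-discharge support call within 72 hours after discharge and two additional calls within one month of discharge". Day 17 is only the latest first outcome call. The safety text also presents the calls as an example and leaves its list of sources open.
- **Bunched calls are unlikely.** All three can fall within 23 - 17 = 6 days, but only in 7 of the 3,150 combinations (0.2%).
- **No mismatch with the parent trial is shown.** The Background gives that trial's nominal 7-day assessment without a window, and no comparison with it is planned.
- **Late preparedness scores need not reflect more specialist calls.** No minimum interval is set between those calls, so more than one could precede an assessment on day 7 itself.

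None of this answers the early 30-day call. A later specialist call might bring an event to light, but it goes to the caregiver, and the log fields in Section 7 include neither acute-care days nor adverse events. The chart variables listed in Section 7 come from SNF records and do not include hospital use after discharge. The synopsis rationale mentions a 60-day questionnaire, but both schedules and Section 7 stop at 30 days, so it cannot be relied on to complete the count.

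**Conclusion.** The point holds, chiefly at the last contact. An in-window 30-day call can leave up to 7 of the 30 days unobserved, both for the acute-care outcome and for adverse events found through the scheduled calls. The likely effect is at most about one patient in 20 under the even-spread assumption, and none if calls are made on day 30 or later. In a study whose only product is descriptive summaries, an outcome with unequal and unstated follow-up is still worth correcting.

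Two lesser points also stand: a call on days 14-17 or 23-28 has no rule assigning it to a contact, and preparedness labelled 7-day may date from day 17.

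A reader might go further and infer that ordered windows would guarantee evenly spaced safety surveillance. They would not. The longest permitted gaps, 28 - 4 = 24 days and 37 - 14 = 23 days, come from the width of the windows and would remain.

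The conclusion assumes that the tolerances in Section 6c govern the calls and that no unstated procedure completes the 30-day count after an early call.

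**What to change.** 1. Open the final data-collection window no earlier than day 30, for example days 30-37, and word the acute-care question to cover discharge to day 30 whatever the call date. If a participant is called sooner, re-contact them to complete the 30-day count and ask about events since the call. If that fails, report the number of days observed.
2. Make the three windows ordered and non-overlapping, for example days 4-13, 14-28 and 30-37, so that each call belongs to one contact.
3. Still make a 7-day call that is late. Flag it and show it separately in the CTM-15 and caregiver preparedness summaries.
4. Align the safety text in Section 7a with the revised schedule.

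The cost is an edit to the schedule headings and the call tracker, plus a few re-contacts. In the example, the first window shrinks from 14 to 10 days and the last from 15 to 8, so some calls will be classed as out of window. With 20 dyads, each such call is 1/20 = 5% of the sample. No data are lost, because those calls are still made and reported.

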## 2. PROTOCOL SYNOPSIS

Study Title	Adapting Connect-Home Transitional Care to Fit the Unique Needs of Persons with Alzheimer's Disease and Other Dementias and their Caregivers: A Pilot Study
Funder	National Institute of Nursing Research
Clinical Phase	Phase I
Study Rationale	
The proposed study will examine the feasibility and acceptability of Connect-Home Plus, a transitional care intervention, targeting Skilled Nursing Facility (SNF) patients with Alzheimer's disease and related dementias (ADRD) who discharge to home and their primary caregivers. The study will be set in two North Carolina SNFs and in the patient's home (during intervention periods only). Using a single-arm, post-test-only trial design, SNF patient and caregiver pairs will be enrolled in a study to prepare for discharge to home-based care and implement plans for home-based care after SNF discharge. The study will describe the feasibility and acceptability of Connect-Home Plus and to estimate the impact of Connect-Home Plus on their outcomes in 7 and 30 days.
 
Patients will be identified by consultation with SNF clinical staff and medical record review. After informed consent, baseline enrollment surveys will be collected for patients and caregivers. Additionally, a medical record review for data related to continued health outcomes will be conducted for patients. Telephone questionnaires will be used to survey patients and caregivers at 7, 21, and 60 days after patients return home.

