#### Variables that will be abstracted from medical charts

Patient data collected from SNF medical records include: age, sex, race, ethnicity, health insurance status (Medicare/Medicaid Advantage/Medicare fee-for-service/private), living arrangements before index hospitalization, educational attainment, medical history (primary diagnosis in the hospital discharge summary, hospital care (critical care, surgery and length of stay), depression (Minimum Data Set section D), function (Minimum Data Set section GG), cognitive status (Minimum Data Set section C or the CPS score, SNF care (i.e., SNF length of stay, urgent or acute treatment while in the SNF), discharge destination. Using the problem list in the medical record, we also will calculate the Charlson Comorbidity Index scores for each patient.

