- Dementia Quality of Life-Proxy measure (DEMQOL-Proxy). When the patient is unable to rate their quality of life, the quality of life will be rated by their caregiver, using the Dementia Quality of Life-Proxy measure.(33) The score range is 31-124 with higher scores indicating better quality of life.
- Self-Reported Days of ED or Hospital Use 30 Days After Skilled Nursing Facility Discharge. Patient's days of acute care use will be measured using the self-reported number of combined number of days the patients pends in the Emergency Department (ED) or hospital in 30 days after SNF discharge.(19)
- Zarit Caregiver Burden Scale. Caregiver burden will be measured using the Zarit Caregiver Burden Scale, which includes 12 items on a five-point scale, measuring caregiver perceptions that "caregiving has an adverse effect on their emotional, social, financial, physical and spiritual functioning."(34) Scores range 0-48; higher scores are associated with depression and social isolation.
- Distress Thermometer. Caregiver distress will be measured using the Distress Thermometer, which includes 1 item on an 11-point scale, measuring negative affect (e.g., sadness and fear) related to caregiving for a severely ill person. Score ranges 0-10, with scores >4 associated with poor coping and depression.(35)

a. Safety Evaluations

- Study progress and safety will be reviewed monthly (and more frequently if needed). Progress reports will include patient and caregiver recruitment, retention/attrition, and adverse events. In addition, safety evaluation will include (1) whether adverse event rates are consistent with pre-study assumptions; (2) reason for dropouts from the study; (3) whether all participants met entry criteria; (4) whether continuation of the study is justified on the basis that additional data are needed to accomplish the stated aims of the study; and (5) conditions whereby the study might be terminated prematurely.
- An adverse event (AE) is any untoward medical occurrence in a subject temporally associated with participation in the clinical study or with use of the experimental agent being studied. An adverse finding can include a sign, symptom, abnormal assessment or any combination of these. A Serious Adverse Event (SAE) is any adverse event that results in one or more of the following outcomes:
  - Death
  - A life-threatening event
  - Inpatient hospitalization
  - A persistent or significant disability/incapacity

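### The 30-day ED/hospital-days outcome is asked once, in a window that opens on day 23, so a compliant early call leaves 1 to 7 days uncounted; separately, Section 5d omits the planned-readmission exclusion stated in Sections 6a and 11.

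*Combined protocol and SAP*

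**What the plan says.** Section 7, Outcome Measures, defines the outcome as the "self-reported number of combined number of days the patients pends in the Emergency Department (ED) or hospital in 30 days after SNF discharge". The counted period is therefore fixed at 30 days.

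In the patient schedule in Section 6c, the row "Hospital and ED use assessment" carries a single mark, in the column "30 Days Post-Discharge (+/- 7 days". The caregiver schedule has no such row.

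For other contacts and sources, the plan says:

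- **Calls.** Section 7a states "We will be calling the patient and caregiver at 7, 21 and 30 days". Sections 5a, 6, 7 and 10 give the same three time points.
- **Chart abstraction.** Under Data Collection Procedures, "the RC will use a standardized tool to abstract data from the medical record in the SNF". The variable list that begins "Patient data collected from SNF medical records include" contains no ED or hospital use after discharge.
- **Specialist's log.** The list that begins "Data collected from the Call-back log will include" does not include ED or hospital use.
- **Synopsis.** It says "a medical record review for data related to continued health outcomes will be conducted for patients" without naming the record. It also mentions a survey at 60 days, which the schedule does not contain.

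On eligibility, Section 5d gives inability to speak English as the only patient exclusion, and so does the synopsis. Sections 6a and 11 give a different one: a planned hospital readmission in the next 30 days, on the ground that it would distort outcome assessment.

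**The concern.** A symmetric window suits measures of current state, such as quality of life or caregiver burden. It does not suit a cumulative count over a fixed period: a respondent called on day 23 cannot report days 24 to 30. With accurate recall, an early call can lose days but never add any, so its error has one direction. Observation time can also differ between patients in a sample of 20, and nothing in the analysis section allows for that.

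Early calls are plausible. The day-21 window (+/- 7) runs from day 14 to day 28, so one contact on days 23 to 28 would satisfy both the day-21 and the day-30 windows.

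The eligibility mismatch bears on the same outcome. A patient with a planned readmission is eligible under Section 5d and ineligible under Sections 6a and 11. If enrolled, that patient's planned stay would count as acute-care days, although the protocol itself calls such stays distorting. The date from which the next 30 days run is not stated either.

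**Working it through.** **Inputs.** Nominal day 30 with tolerance 7 (Section 6c); outcome period 30 days (Section 7); one assessment (Section 6c); 20 patients (Sections 5c and 8). The plan derives no figure for this outcome, so there is none to reproduce.

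**Window.** 30 − 7 = 23 and 30 + 7 = 37, which is 37 − 23 + 1 = 15 compliant days. Seven of these, days 23 to 29, are early.

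**Loss per patient.** For a call on day d < 30, unobserved days m = 30 − d. If the patient was in the ED or hospital on every one of those days, the mean of 20 falls by m/20. If on none of them, nothing changes.

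| Call day | Days missed | Share of 30 | Maximum fall in mean (days) |
|---|---|---|---|
| 23 | 7 | 23.3% | 0.35 |
| 24 | 6 | 20.0% | 0.30 |
| 25 | 5 | 16.7% | 0.25 |
| 26 | 4 | 13.3% | 0.20 |
| 27 | 3 | 10.0% | 0.15 |
| 28 | 2 | 6.7% | 0.10 |
| 29 | 1 | 3.3% | 0.05 |

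**Loss over the sample.** Full observation is 20 × 30 = 600 person-days. The number of early calls, k, is not in the documents, so the range is shown; k early calls lose between k × 1 and k × 7 days.

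| k | Person-days lost | Share of 600 |
|---|---|---|
| 1 | 1 to 7 | 0.2% to 1.2% |
| 5 | 5 to 35 | 0.8% to 5.8% |
| 10 | 10 to 70 | 1.7% to 11.7% |
| 20 | 20 to 140 | 3.3% to 23.3% |

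If calls were spread evenly over the 15 days (an assumption), the mean loss would be (7+6+5+4+3+2+1)/15 = 28/15 = 1.87 days per patient.

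**Could another source complete the count?**

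- *Chart abstraction:* as described it draws on the SNF record, and no listed variable is post-discharge use. The synopsis record review and the second abstraction row at day 30 name no post-discharge source. This route is unclear rather than ruled out.
- *Adverse event reporting:* inpatient stays are serious adverse events, but after discharge they are learned from patient or caregiver reports. The last scheduled call is the same day-30 call. An ED-only visit is not a listed serious outcome.
- *Specialist's log:* acute-care use is not among its items.
- *Day 60:* the synopsis mentions a survey then, and the synopsis and Section 5b allow participation up to 60 days. No assessment at that time is scheduled.

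**Eligibility lists side by side.** Section 5d and the synopsis list language only; Sections 6a and 11 list planned readmission. No rate of planned readmission is given, so the effect cannot be sized.

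**The case against.** The strongest reply concerns weight. The study disclaims efficacy, uses descriptive statistics only, and attaches no test or threshold to this outcome. Contact is nominally on day 30, with 7 days as tolerance, and the largest loss needs every call on day 23, which nothing suggests will happen. All of this stands, and it is why the effect is called modest. It does not make the count right when a call is early.

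A second reply is that late calls may offset early ones. On days 31 to 37, respondents could report 1 to 7 days beyond the period if recall is not cut at day 30. Section 7 fixes the period, so a late call made to that definition is correct. But no interview wording is given, and the respondents are cognitively impaired patients or their caregivers. The one-way error is therefore claimed for early calls only; the net direction over the whole window is not established.

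Third, narrowing the window has a price. One lost interview forfeits 30 person-days (30/600 = 5%), more than four calls on day 23 (4 × 7 = 28). Section 6 lets the caregiver answer when the patient cannot, but the synopsis calls this outcome patient-reported and the caregiver schedule has no row for it. This favours repeating the question over restricting the window.

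On eligibility, it is fair to say that the two operational sections agree and Section 5d is merely silent. But Section 5d is the study-population list, and a reader relying on it would enrol such a patient.

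**Conclusion.** Both parts hold. A compliant call on days 23 to 29 leaves 7 to 1 of the 30 days unobserved, and no source is clearly arranged to recover them. The cost is at most 0.05 to 0.35 day on the mean of 20 for each affected patient. The total depends on call dates and on acute-care use in the missed days, neither of which the documents give. The window arithmetic needs no assumption about event rates; the even-spread figure is illustrative only.

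The consequence is limited to one descriptive secondary outcome. The primary feasibility and satisfaction outcomes are unaffected. It should still be corrected, because the correction is cheap and hospital readmission is named in the secondary objective. The exclusion lists do contradict one another, by an amount that cannot be quantified.

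**What to change.** For the hospital and ED item only, either:

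- repeat the question on or after day 30 for any patient whose day-30 interview took place earlier; or
- give the item its own window of day 30 to day 37 (+7/−0).

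In both cases the interview should state the counted period as the 30 days from discharge, as Section 7 already defines it. The other day-30 measures keep +/- 7 days. Either option brings the unobserved days for a completed item from a maximum of 7 to 0. If a post-discharge record is meant to complete the count, name it. State whether the caregiver may answer this item.

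Reconcile the patient exclusions in Section 5d and the synopsis with Sections 6a and 11, and state when the next 30 days begin. The 60-day references should be reconciled with the schedule at the same time.

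The cost is a wording amendment, plus either a one-question call to patients interviewed early or a window for this item that shrinks from 15 days to 37 − 30 + 1 = 8 days, with some risk of lost interviews. The repeat question carries less of that risk, since the early answer is already in hand. Reconciling the lists needs no new data collection.
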